NGS	Next Generation Sequencing
NTP	National TB Programme
QA	Quality Assurance
QC	Quality Control
QMS	Quality Management System
RA	Regulatory Authority
RBM	Risk Based Monitoring
RM	Risk Management
RIF	Rifampicin
SAE	Serious Adverse Event
SAP	Statistical Analysis Plan
SNRL	Supranational Reference Laboratory
SOP	Standard Operating Procedure
TB	Tuberculosis
TMF	Trial Master File
WHO	World Health Organization
XDR	Extensively Drug-resistant

Protocol Synopsis

Title	Phase II: Multicentre Clinical Study to Assess the Performance of the Xpert MTB/XDR Assay for INH- and Second-line Resistance Detection
Short title	Xpert MTB/XDR Clinical Evaluation
Protocol version and date	v1.1 05-NOV-2018
Background and rationale	Evidence of the clinical diagnostic accuracy and operational characteristics of the Xpert MTB/XDR assay is needed to comprehensively evaluate Xpert MTB/XDR validity and inform global and national policy decision-making.
Objectives	
Primary objectives
 
1.1 Estimate the diagnostic accuracy of the Xpert MTB/XDR assay for INH and ETH resistance detection
 
1.2 Estimate the diagnostic accuracy of the Xpert MTB/XDR assay for fluoroquinolone resistance detection
 
1.3 Estimate the diagnostic accuracy of the Xpert MTB/XDR assay for second-line injectable resistance detection
 
1.4 Assess Xpert MTB/XDR technical performance, including non-determinant rates, ease of use and other systems operational characteristics.
 
Secondary objectives
 
2.1 Assess additional Xpert MTB/XDR performance characteristics, including direct performance versus performance on cultured samples, performance between sites, by smear result, by gene target and compared to Hain MTBDRplus and MTBDRsl

Study design	Multicentre, cross-sectional diagnostic accuracy study
Study sites/setting	Clinical sites with high rates of drug-resistant TB in India, Moldova and South Africa
Study population	Patients with pulmonary TB symptoms and at least one DR-TB risk factor will be screened by Xpert MTB/RIF or Ultra. Patients with a clear TB-positive and RIF-resistant or RIF-sensitive result by Xpert MTB/RIF or Ultra and who consent to study procedures will be tested by Xpert MTB/XDR. An anticipated 284 TB-positive and 316 additional RIF-resistant patients will be enrolled in this study.
Eligibility criteria	
Screening criteria:
 
 • Age 18 years and above • Symptoms suggesting pulmonary TB, i.e. persistent cough (generally ≥ 2 weeks or as per local definition of TB suspect) and at least one risk factor for DR-TB 
Inclusion criteria:
 
 • A clear TB-positive and RIF-resistant or -sensitive result by Xpert MTB/RIF or Xpert MTB/RIF Ultra • Provision of Informed Consent • Production of an adequate quantity (≥ 3mL) of sputum
Primary endpoints	
1.1 Sensitivity and specificity estimates for INH and ETH resistance detection
 
1.2 Sensitivity and specificity estimates for fluoroquinolone resistance detection
 
1.3 Sensitivity and specificity estimates for second-line injectable resistance detection

	1.4 Assessment of Xpert MTB/XDR technical performance
Secondary endpoints	2.1 Assessment of additional Xpert MTB/XDR performance characteristics
Study duration	10 weeks for IVD testing, with an additional 15 weeks to complete culture, DST, and NGS
Time schedule	IRB/IEC Approval: June-December 2018 Shipment: January-March 2019 Training: March 2019 All Testing: April-September 2019 Data Cleaning: September-October 2019 Preliminary Analysis: October 2019
GCP statement	This study will be conducted in compliance with the protocol, the Declaration of Helsinki, ICH-GCP, ISO 13485: 2016 (if applicable) as well as all national legal and regulatory requirements.

Project Timeline

▼ Clinical Studies	528 d	Oct 25, 2017 at...	Nov 1, 2019 at...
▼ Study Conception and Preparation	310 d	Oct 25, 2017 at...	Jan 1, 2019 at...
Write and Review Clinical Protocols	24 w	Oct 25, 2017 at...	Apr 10, 2018 at...
Site Selection and Contracts	24 w	Apr 11, 2018 at...	Sep 25, 2018 at...
Preparation of TMF	24 w	Apr 11, 2018 at...	Sep 25, 2018 at...
IRB Approvals	14 w	Sep 26, 2018 at...	Jan 1, 2019 at 5...
▼ Study Conduct	330 d	Jul 30, 2018 at...	Nov 1, 2019 at...
▼ Phase I: Lab Validation	170 d	Jul 30, 2018 at...	Mar 22, 2019 at...
Strain Selection	12 w	Jul 30, 2018 at...	Oct 19, 2018 at...
Shipment and Customs Clearance	8 w	Oct 22, 2018 at...	Dec 14, 2018 at...
Site Training and Initiation	1 w	Jan 21, 2019 at...	Jan 25, 2019 at...
Testing, Data Entry and Cleaning	4 w	Jan 28, 2019 at...	Feb 22, 2019 at...
Analysis	2 w	Feb 25, 2019 at...	Mar 8, 2019 at...
Data Review and Report	2 w	Mar 11, 2019 at...	Mar 22, 2019 at...
▼ Phase II: Clinical Trial	240 d	Dec 3, 2018 at...	Nov 1, 2019 at...
Import Permits	8 w	Dec 3, 2018 at...	Jan 25, 2019 at...
Shipment and Customs Clearance	7 w	Jan 28, 2019 at...	Mar 15, 2019 at...
Site Training and Initiation	2 w	Mar 18, 2019 at...	Mar 29, 2019 at...
Testing of Samples	10 w	Apr 1, 2019 at 8...	Jun 7, 2019 at 5...
Completion of Culture/DST/NGS	15 w	Jun 10, 2019 at...	Sep 20, 2019 at...
Data Entry and Cleaning	2 w	Sep 23, 2019 at...	Oct 4, 2019 at 5...
Data Analysis	2 w	Oct 7, 2019 at 8...	Oct 18, 2019 at...
Data Review and Report	2 w	Oct 21, 2019 at...	Nov 1, 2019 at...

1 Introduction

FIND and partners intend to address the need for a multi- and extensively drug-resistant tuberculosis (M/XDR-TB) diagnostic solution for patients in settings with a high burden of drug-resistant tuberculosis (DR-TB) through the development, evaluation and introduction of an Xpert MTB/XDR assay.

1.1 Study Rationale

Evidence of the clinical diagnostic accuracy and operational characteristics of the Xpert MTB/XDR assay is needed to comprehensively evaluate assay validity in settings of intended use and inform global and national policy decision-making.

1.2 Potential Risks and Benefits

This study has no known medical risks for participants. Sample inclusion in this study will not affect TB or M/XDR-TB patient routine care and treatment. No clinical decisions will be made from Xpert MTB/XDR results. The possibility of unknown or unforeseen risk from specimen collection and diagnostic testing is minimal. Knowledge gained from this study may benefit patient communities by improving DR-TB diagnosis. Given the minimal risks associated with this study and the potential benefits to society and individuals, the benefits outweigh the aggregated risks.

If unforeseen risks are recognized during the study, then FIND, study partners, Institutional Review Boards (IRBs)/Independent Ethics Committees (IECs), and participants must be provided with relevant information.

1.3 Background

In recent years, tuberculosis (TB) control efforts have been complicated by the rise and spread of MDR-TB, or TB that is resistant to the first-line drugs isoniazid (INH) and rifampicin (RIF), and XDR-TB, or MDR-TB that has developed additional resistance to a fluoroquinolone and any of the injectable compounds [amikacin (AMK), kanamycin (KAN) and/or capreomycin (CAP)]^{1,2}. The rapid diagnosis and appropriate treatment of M/XDR-TB is essential to prevent significant morbidity, mortality and further transmission of disease. For treatment of uncomplicated MDR-TB, the World Health Organization (WHO) recently endorsed a 6-9 month treatment regimen, thereby replacing conventional 18-24 month regimens³. The fluoroquinolones and second-line injectables are key components of the 6-9 month regimen, and so it is necessary to rule-out resistance to these compounds prior to treating patients with the shorter regimen.

The Xpert MTB/RIF assay (Cepheid, Sunnyvale, CA) is an integrated, automated, cartridge-based system for MDR-TB diagnosis that uses the GeneXpert instrument platform. WHO confirmed evidence to support the widespread use of the Xpert MTB/RIF assay in 2010 and the assay has since been widely used in TB programs⁴, but it is only capable of identifying *Mycobacterium tuberculosis* (Mtb) and detecting RIF resistance, and so it does not provide the comprehensive resistance profile necessary to determine if the shorter TB treatment regimen is appropriate for certain patients. Conventional diagnosis of TB drug resistance relies upon the slow growth of Mtb in solid or liquid media, only then followed by resistance testing to determine phenotypic drug resistance. These conventional drug susceptibility testing (DST) methods can take several weeks to yield results⁵⁻⁶, require significant laboratory infrastructure and training, and are potentially biohazardous. In view of the inadequacy of these conventional tests for resistance detection, the development of rapid tests for INH and second-line resistance detection has become a research and implementation priority.

Rapid diagnostics for second-line drug resistance detection identify mutations in the *gyrA* and *gyrB* genes⁷, associated with fluoroquinolone resistance, and *rrs* and *eis* gene regions, associated with second-line injectable resistance (with *eis* promoter mutations exclusively associated with KAN resistance)⁸. Recently, a novel GeneXpert cartridge was developed to detect mutations occurring in these genes, as well as in the *katG* and *inhA* gene regions, associated with INH resistance⁹. A Research Use Only (RUO) version of the Xpert MTB/XDR cartridge showed promising performance for INH and second-line resistance detection in a clinical evaluation study (sensitivity 92.7-98.1%; specificity 94.3-99.6%)¹⁰. The assay chemistry has since been improved and additional gene targets have been added to the assay to improve the detection of INH resistance (i.e. *fabG1* and *ahpC*).

Evidence of assay accuracy from an external laboratory validation using a well-characterized set of Mtb strains as well as from large-scale, multicentre clinical studies is needed to confirm the validity of the most recent Xpert MTB/XDR assay for INH and second-line resistance detection, and to recommend its use in diverse clinical settings. The focus of this protocol is the multicentre clinical evaluation.

2 Study Objectives and Endpoints

Objectives	Data Collected	Endpoint
Primary		
1.1 Estimate the diagnostic accuracy of the Xpert MTB/XDR assay for INH and ETH resistance detection , for a clinically diverse set of TB samples, with phenotypic DST and katG , fabG1 , ahpC and inhA	284 Xpert MTB/RIF TB-positive and 316 RIF-resistant clinical samples tested by Xpert MTB/XDR, phenotypic DST and NGS	1.1 Sensitivity and specificity estimates for INH and ETH resistance detection


sequencing results as a composite reference standard.
 
1.2 Estimate the diagnostic accuracy of the Xpert MTB/XDR assay for fluoroquinolone resistance detection, for a clinically diverse set of TB samples, with phenotypic DST and gyrA and gyrB sequencing results as a composite reference standard.
 
1.3 Estimate the diagnostic accuracy of the Xpert MTB/XDR assay for second-line injectable resistance detection, for a clinically diverse set of TB samples, with phenotypic DST and rrs and eis sequencing results as a composite reference standard.
		
1.2 Sensitivity and specificity estimates for fluoroquinolone resistance detection
 
1.3 Sensitivity and specificity estimates for second-line injectable resistance detection

1.4 Assess Xpert MTB/XDR operational aspects and ease of use, including Xpert MTB/XDR non-determinant rates.
	
Completion of laboratory CRFs for all samples and completion of user-appraisal questionnaires by at least two operators per site at two different timepoints (after training and after study completion)
	
1.4 Assessment of Xpert MTB/XDR operational aspects and ease of use

Secondary		

2.1 Assess additional Xpert MTB/XDR performance characteristics:
 
 ○ Direct performance versus performance on cultured samples ○ Performance between sites ○ Performance by smear result ○ Performance by gene target ○ Performance compared to Hain MTBDR_{plus/sl} ○ Performance by patient HIV status ○ Performance by patient pre-treatment status ○ Performance as reflex test to Ultra or MTB/RIF assay 	
Smear, culture, NGS, MTBDR_{plus}, MTBDR_{sl} and two Xpert MTB/XDR results (direct from sputum and from cultured strain) for each clinical sample tested
	
2.1 Assessment of additional Xpert MTB/XDR performance characteristics

3 Study Design

3.1 General Design

Multicentre clinical diagnostic accuracy study.

3.2 Scientific Rationale for Study Design

The current study is part of a two-phase project.

- Phase 1 (the current study) is an analytical study to validate and expand upon the Xpert MTB/XDR analytical data that the manufacturer (Cepheid, Sunnyvale, California) has compiled for internal validation, CE-IVD marking and/or other regulatory purposes.
- Phase 2 is a clinical study to determine the diagnostic accuracy at intended settings of use.

The two phases will provide complementary pieces of evidence to address the study objectives.

The main purpose of this clinical study is to confirm accuracy estimates from the external laboratory validation and ensure that Xpert MTB/XDR diagnostic performance characteristics will be consistent at sites of intended use. Assay performance when testing sputum samples (direct testing) and cultured isolates (indirect testing), assay performance compared to the Hain MTBDR*plus* and MTBDRs/ (Hain Lifesciences GmbH) line probe assays (LPAs), and assay error and failure rates and device operational characteristics will also be assessed during this phase of the study.

In order to address clinical study objectives quickly and efficiently, this study will first assess Xpert MTB/XDR performance for Xpert MTB/RIF MTB-positive samples from patients prospectively enrolled in the study. Focusing the study on Xpert MTB/RIF MTB-positive samples is in line with the intended use of the assay as a reflex, or follow-up, test to any Xpert MTB/RIF or Ultra MTB-positive result. This will also allow for an assessment of assay performance for INH resistance detection among all MTB-positive samples including INH mono-resistant, as this population might be different from a largely RIF-resistant population. However, to ensure numbers are adequate for an assessment of Xpert MTB/XDR assay performance for second-line resistance detection, once sufficient MTB-positive, RIF-sensitive samples have been tested, a subset of solely Xpert RIF-resistant samples will be tested until enrolment targets are met (see section 9.1 and Appendix 4: Sample Requirement to Achieve Target Sample Size).

3.3 Study Setting

Study sites will be geographically diverse and representative of regional epidemics (i.e. TB and resistance prevalence, HIV co-infection, lineage distribution).

Laboratories will represent the intended setting of use for the Xpert MTB/XDR assay,

i.e. laboratories that routinely process a large number of DR-TB samples and wherein second-line drug resistance may be suspected. Site preference will be given to countries/sites that are able to be early adopters (in terms of both political will and financial means) and sites with strong National TB Programme (NTP) relationship and global reach in order to gain visibility and encourage buy-in to facilitate national and global policy uptake. Participating sites must also have a sufficiently high throughput of TB clinical samples, and have access to phenotypic DST and NGS testing to allow for the efficient assessment of Xpert MTB/XDR assay performance.

Regional distributions and country options (to be confirmed):

- Africa (South Africa)
- Asia (India)
- Eastern Europe (Moldova)

3.4 End of Study Definition

Phase II will be considered completed once all *in vitro* diagnostic (IVD) testing has completed and all culture, DST and NGS results have been returned for at least 284 TB-positive and 316 additional RIF-resistant clinical samples, and all user appraisal questionnaires have been completed at the three clinical sites.

4 Study Population and Eligibility

Individuals who have one or more risk factors for DR-TB presenting to participating centres will be screened by Xpert MTB/RIF or Ultra. Those who test MTB-positive by Xpert MTB/RIF or Ultra at the study sites will be asked to participate. Once at least 360 MTB-positive patients have been tested, an additional subset of Xpert MTB-positive, RIF-resistant patients (n=400) will also be asked to participate in this study. Individuals will be recruited at outpatient clinic settings and inpatient hospital settings. Individuals will be asked by non-study clinicians or staff if they would be interested in participating in the study. Interested individuals will be referred to study personnel for additional information and screening, if appropriate. HIV-positive individuals and HIV-negative individuals will be included in this study.

Prospective approval of protocol deviations to recruitment and enrolment criteria, also known as protocol waivers or exemptions, is not permitted.

4.1 Inclusion Criteria:

Patients meeting the following criteria will be screened by Xpert MTB/RIF or Xpert MTB/RIF Ultra:

- Age 18 years or above;
- Symptoms suggesting pulmonary TB, i.e. persistent cough (generally ≥ 3 weeks or as per local definition of TB suspect), **and** at least one of the following:
 - Previously received >1 month of treatment for a prior TB episode **or**
 - Failing TB treatment with positive sputum smear or culture after ≥ 3 months of a standard TB treatment **or**
 - Had close contact with a known drug-resistant TB case **or**
 - Newly diagnosed with MDR-TB within the last 30 days **or**
 - Previously diagnosed with MDR-TB and failed TB treatment with positive sputum smear or culture after ≥ 3 months of a standard MDR-TB treatment regimen

Patients meeting the above criteria will be screened by Xpert MTB/RIF or Xpert MTB/RIF Ultra. TB patients meeting the following criteria will be included in the study:

- A clear Mtb-positive and RIF-resistant or RIF-sensitive result by Xpert MTB/RIF or Xpert MTB/RIF Ultra
- Provision of informed consent;
- Production of an adequate quantity ($\geq 3\text{mL}$) of sputum

4.2 Exclusion Criteria:

Participants will be excluded from the study if informed consent is not provided.

4.3 Early Exclusions

Participants who have provided consent and who are enrolled, but who do not provide an adequate quantity of sputum at the start of the study, will be classified as early exclusions; each will be removed from the study and a new study subject enrolled. Participants who are classified as early exclusions will be referred to the appropriate local health service for TB evaluation and care. If positive for Mtb, results of conventional microbiological tests (e.g., sputum smear microscopy, mycobacterial cultures, and/or Xpert MTB/RIF) will be reported to appropriate local health authorities in accordance with local public health reporting regulations. Study data for participants who are classified as early exclusions will not be used for any final analyses.

4.4 Participant Discontinuation/Withdrawal from Study

A participant may be withdrawn at any time at the discretion of the investigator for safety, behavioural, compliance, or administrative reasons.

If the participant withdraws consent for disclosure of future information, the sponsor may retain and continue to use any data collected before such a withdrawal of consent.

If a participant withdraws from the study, he/she may request destruction of any samples taken and not tested, and the investigator must document this in the site study records.

See Schedule of Assessments for data and/or samples to be collected at the time of study discontinuation and follow-up and for any further evaluations that need to be completed.

5 Study Intervention

Study Intervention is defined as any investigational intervention(s), marketed product(s), or medical device(s) intended to be used with a study participant according to the study protocol.

5.1 *in vitro* Diagnostics

The IVD manufactured for FIND use in this study is the Xpert MTB/XDR assay. The Investigational Use Only (IUO) product is intended for the detection of Mtb and mutations associated with INH, ETH and second-line drug resistance. Likewise, the 10-color GeneXpert system provided for this study should only be used for testing IUO cartridges and study samples. The investigational product and 10-color system will be strictly accounted for, including receipt and inventory, storage, use during the trial, and return or disposal, as detailed in the Study Manual for this study.

Other IVDs (not manufactured for FIND) obtained for use in this study are:

- Xpert MTB/RIF assay and/or the Xpert MTB/RIF Ultra assay
- Hain MTBDR*plus* assay
- Hain MTBDR*s/* assay

Instructions for use of these assays will be provided in the SOPs for this study.

Any IVD incidents, including those resulting from malfunctions of the IVD, must be detected, documented and reported by the investigator throughout the study (see section 8.1.4).

5.2 Preparation/Handling/Storage/Accountability

5.2.1 Acquisition

Procurement of the Xpert MTB/XDR assays will be done through FIND, which will coordinate shipments from the manufacturer. It is the responsibility of each laboratory to maintain an updated inventory of the study materials and to inform FIND immediately if additional materials are required.

It is expected that the respective countries will require import permits for receiving the investigational materials. The laboratory is responsible for obtaining relevant import permits in a timely manner. The sponsor and IVD manufacturer may support the laboratory to obtain import permits. Upon arrival of each new shipment of Xpert assays or reagents, the laboratory will conduct and document an incoming quality check following the Manual of Procedures. New lots may only be used after this quality check is successfully passed.

5.2.2 Handling

The investigator or designee must confirm appropriate temperature conditions have been maintained during transit for all Xpert MTB/XDR assays received and any discrepancies are reported and resolved before use of the Xpert MTB/XDR assay.

Only those participants enrolled in the study may have their samples tested by the Xpert MTB/XDR assay, and only authorized and trained staff may operate the Xpert MTB/XDR assay. Testing using the investigational product will be performed according to the manufacturer's instructions outlined within the SOP.

5.2.3 Storage

Procedures for product storage and disposal will be described in the SOP. All Xpert MTB/XDR assays must be stored in a secure, environmentally controlled, and monitored (manual or automated) area in accordance with the labeled storage conditions with access limited to the investigator and authorized site staff.

5.2.4 Accountability

The investigator, institution, or the head of the medical institution (where applicable) is responsible for Xpert MTB/XDR accountability, reconciliation, and record maintenance (i.e., receipt, reconciliation, and final disposition records).

Further guidance and information for the final disposition of unused study interventions are provided in the SOP.

5.3 Minimization of Error and Bias

5.3.1 Patient Selection

A consecutive series of Xpert MTB/RIF MTB-positive patients (n=284) will be enrolled in this study, followed by an additional, consecutive series of Xpert MTB/RIF RIF-resistant patients (n=316) between the three countries with participating clinical sites. Enrolment will be based upon clearly defined eligibility criteria.

Analyses will be conducted for relevant sub-groups of the enrolled TB patient population (i.e. smear status for TB, drug-resistance profile, mutations detected, etc.), which may be considered to be indicators of disease severity.

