6.1.2 Study Workflow

Study flow is shown in Figure 1. All available Xpert MTB/RIF TB-positive samples will be tested in this study (i.e. consecutive patient samples) until sample size targets are met. All molecular assays will be performed in accordance with SOPs provided by the manufacturers. Specimen handling and processing by routine tests will be carried out according to NTP local policies and standards.

Samples will first be tested by Xpert MTB/RIF or Ultra, as part of routine diagnostic procedures. This Xpert MTB/RIF step will act as a screening tool for trial enrolment. Participants testing positive for MTB by Xpert MTB/RIF will be asked to volunteer for the Xpert MTB/XDR trial. This (testing of specimens from TB-positive samples) is in line with the intended use of the XDR assay as an add-on test to the Xpert MTB/RIF assay.

[figure not shown]
A staged enrolment will proceed: Stage 1 will enrol 360 MTB-positive participants, irrespective of RIF resistance/sensitivity. Once enrolment is complete, Stage 2 will enrol 400 MTB-positive RIF-resistant participants (see section 9.1 and Appendix 4: Sample Requirement to Achieve Target Sample Size). This staging is designed to better evaluate Xpert MTB/XDR sensitivity for second-line resistance detection.

In order to efficiently assess the diagnostic performance of the Xpert MTB/XDR assay, participants will be asked to provide ≥ 3 ml of sputum (either a single sputum or two consecutively collected and pooled sputa). Samples will be homogenized and split for testing.

The Xpert MTB/XDR assay and acid-fast bacilli smear will be performed on the direct sample. 2ml of sputum will be decontaminated and used for MGIT and LJ culture.

Following direct testing, phenotypic MGIT DST will be performed for all culture-positive samples for INH, RIF, fluoroquinolone (moxifloxacin and levofloxacin), AMK, ETH (ethionamide), KAN and CAP. Cultured samples will also undergo subsequent molecular testing by LPA and targeted NGS of relevant gene regions (*katG*, *inhA*, *fabG1*, *ahpC*, *gyrA*, *gyrB*, *rrs*, and *eis*) and another Xpert MTB/XDR assay. NGS will be performed from the culture isolate to obtain sequencing reads of high quality.

Figure 1. Phase II sample flow

≥ 3ml of sputum is required for the trial. This can be achieved through an individual sputum or pooling of serially collected sputa, homogenized with glass beads.

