Appendix 4: Sample Requirement to Achieve Target Sample Size

	MTB+ group*		Additional RIF-R group		TOTAL
Samples Tested	100%	360	100%	400	760
Invalid Xpert Ultra results	1%	4	1%	4	8
Culture-contaminated	10%	36	10%	40	76
Molecular-test non-determinant*	10%	36	10%	40	76
Included**	79%	284	79%	316	600
INH-resistant	29%	82	99%	313	395
INH-sensitive	71%	202	1%	3	205
FQ-resistant	5%	14	25%	79	93
FQ-sensitive	95%	270	75%	237	507
AMK/CAP-resistant	2%	6	9%	28	34
AMK/CAP-sensitive	98%	278	91%	288	566
KAN-resistant	1%	3	21.5%	68	71
KAN-sensitive	99%	281	78.5%	248	529

*Assume 23% of TB-positive samples are RIF-R based upon previous studies and data from these regions^{11,13}.

**We assume 29% INH resistance, 5% FQ resistance and 1-2% second-line injectable (AMK, KAN and CAP) resistance among TB-positive patients based upon previous studies and data from these regions^{11,13}. Testing 284 TB-positive specimens (based on Xpert MTB/RIF and Ultra-testing) would then be expected to yield 82 INH-resistant but only 14 FQ-resistant specimens and 3-6 second-line injectable-resistant specimens (limiting factor in sample size calculations). This allows for determination of Xpert MTB/XDR performance for INH resistance detection as a reflex test to any TB-positive result, but is not sufficient for determination of Xpert MTB/XDR performance for second-line resistance detection. To efficiently get to a sufficient number of second-line resistant samples, we will supplement this by testing 316 additional RIF-resistant samples. To account for contaminated cultures and invalid/non-determinant Xpert MTB/RIF or Ultra, NGS and Xpert MTB/XDR results, we would inflate these numbers by 21%, leading to a total of 360 TB-positive and 400 additional RIF-resistant samples, i.e. a total of 760 patient samples tested in this study.

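### The synopsis and section 5.3.1 give 284 + 316 as the numbers to enrol, while section 6.1.2 gives 360 + 400; the lower pair are the evaluable counts after the planned 21% loss

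*Protocol*

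**What the plan says.** Two places in the protocol use the smaller pair of numbers for enrolment.

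- Synopsis, study population: "An anticipated 284 TB-positive and 316 additional RIF-resistant patients will be enrolled in this study".
- Section 5.3.1: "A consecutive series of Xpert MTB/RIF MTB-positive patients (n=284) will be enrolled in this study", followed by a consecutive RIF-resistant series of 316.

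Two places use the larger pair.

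- Section 6.1.2: "Stage 1 will enrol 360 MTB-positive participants, irrespective of RIF resistance/sensitivity", and afterwards "Stage 2 will enrol 400 MTB-positive RIF-resistant participants".
- Section 4: "Once at least 360 MTB-positive patients have been tested", then "an additional subset of Xpert MTB-positive, RIF-resistant patients (n=400) will also be asked to participate in this study". The numbers match section 6.1.2, but the verbs are those of testing and inviting, not enrolling.

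Three places explain how the pairs are related. Protocol section 9.1 and SAP section 10 both plan for 760 samples tested and 600 results available for analysis, made up of 284 and 316. Appendix 4 takes off 1% for invalid Xpert Ultra results, 10% for contaminated cultures and 10% for non-determinant molecular tests. It describes the inflation as "leading to a total of 360 TB-positive and 400 additional RIF-resistant samples".

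Section 3.4 defines the study as complete only when culture, DST and NGS results are back for at least 284 and 316 samples.

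**The concern.** The same act, enrolling patients, is given two different sizes. A reader of the synopsis or section 5.3.1 alone is not told that 284 and 316 are counts after losses, and could take them as the points at which recruitment to each stage ends.

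Two things would be affected. The first is the switch between stages: Stage 2 opens when Stage 1 enrolment is complete, so 284 or 360 decides when recruitment is restricted to RIF-resistant patients. The second is the final yield of resistant samples, which sets the precision of every sensitivity estimate. Appendix 4 names the second-line drugs as the limiting factor in the sample size, so a shortfall would matter most for them.

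A shortfall could also come to light late. The timeline allows 10 weeks for testing and a further 15 weeks for culture, DST and NGS to finish, so the number of evaluable samples is not fully known until well after testing ends.

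**Working it through.** **Inputs.** Loss rates and resistance rates by group come from Appendix 4. The assumed sensitivity (90%), assumed INH specificity (98%) and interval method (Wilson score with continuity correction) come from Table 2 of the protocol, repeated in the SAP.

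**Step 1: reproduce the plan's figures.** Total loss is 1% + 10% + 10% = 21%, so 79% is retained.

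- 284 / 0.79 = 359.5, rounded up to 360
- 316 / 0.79 = 400
- 600 / 0.79 = 759.5, rounded up to 760
- In the other direction, 360 × 0.79 = 284.4 and 400 × 0.79 = 316.0

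All three planned totals reproduce. This confirms that 284 and 316 are post-loss counts and 360 and 400 are pre-loss counts.

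**Step 2: evaluable samples if enrolment stopped at 284 + 316.**

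- 284 × 0.79 = 224.4
- 316 × 0.79 = 249.6
- Total 474, which is 126 (21%) short of 600

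Eligibility already requires a clear Xpert MTB/RIF or Ultra result, so the 1% loss may fall before enrolment. The losses could also be applied one after another instead of summed. The alternatives are:

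- no 1% loss, summed: 600 × 0.80 = 480
- all three losses in sequence: 600 × 0.99 × 0.90 × 0.90 = 481
- no 1% loss, in sequence: 600 × 0.90 × 0.90 = 486

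The range is therefore about 474 to 486.

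**Step 3: expected resistant samples at 79% retention.**

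- INH: 0.29 × 224.4 + 0.99 × 249.6 = 312
- Fluoroquinolones: 0.05 × 224.4 + 0.25 × 249.6 = 74
- KAN: 0.01 × 224.4 + 0.215 × 249.6 = 56
- AMK/CAP: 0.02 × 224.4 + 0.09 × 249.6 = 27

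**Step 4: interval width at 90% sensitivity.** With p = 0.90, q = 0.10 and z = 1.96, the limits are

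- lower = [2np + z² − 1 − z√(z² − 2 − 1/n + 4p(nq + 1))] / [2(n + z²)]
- upper = [2np + z² + 1 + z√(z² + 2 − 1/n + 4p(nq − 1))] / [2(n + z²)]

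| Drug | Planned n | Width, points | Printed width | Reduced n | Interval | Width, points |
|---|---|---|---|---|---|---|
| INH | 395 | 6.2 | 7% | 312 | 86.0 to 93.0 | 7.0 |
| FQ | 93 | 13.4 | 13% | 74 | 80.3 to 95.4 | 15.2 |
| KAN | 71 | 15.5 | 16% | 56 | 78.3 to 96.0 | 17.7 |
| AMK/CAP | 34 | 23.4 | 23% | 27 | 71.0 to 97.6 | 26.6 |

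The printed widths equal the differences between the printed whole-number limits, so the fair comparison is between the two computed columns. The increases are 0.8 (INH), 1.8 (FQ), 2.2 (KAN) and 3.2 (AMK/CAP) points.

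**Step 5: INH specificity, the smallest specificity group.** The expected count falls from 205 to 0.71 × 224.4 + 0.01 × 249.6 = 162. At 98%, the width goes from 4.7 to 5.4 points.

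**The case against.** The strongest reply is that the intent is not in doubt and the trial is largely protected. Section 6.1.2, which governs the staging, gives 360 and 400 and refers to section 9.1 and Appendix 4. Section 3.2 refers enrolment targets to the same two places. Section 4 does not open the second group until at least 360 MTB-positive patients have been tested. Section 3.4 would probably not be met by stopping at 600 enrolled with a 21% loss. The synopsis calls its figures anticipated. All of this stands, and it makes the shortfall a possibility, not an expectation. It does not remove the contradiction: section 5.3.1 is not qualified in that way, and section 3.4 governs when the study is complete, not when each stage stops recruiting.

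A second reply is that the lost precision is modest and no threshold depends on it. That is also fair. The plan is one of estimation, SAP section 8 states that no multiple testing of hypotheses will be performed, and the widening is at most about 3 points.

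A reader might go further and infer that none of the Table 2 sensitivity rows would be delivered at the lower numbers. The calculation does not support this. Every row would miss its planned n, but INH at 312 still gives 86 to 93 with a width of 7.0, which is the interval and width printed for it. Only the FQ, KAN and AMK/CAP rows would miss their stated widths.

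**Conclusion.** The inconsistency is real and lies in the labelling. The synopsis and section 5.3.1 present post-loss counts as enrolment targets and contradict section 6.1.2. A reader might infer that the sample-size calculation is wrong, or that the trial is set to finish with 474 evaluable samples. Neither follows: the calculation reproduces in full, and the sections that set out the sample size all point to 760 tested and 600 evaluable.

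The size of the problem, if someone worked from the lower figures, is a loss of about 114 to 126 evaluable samples (600 − 486 to 600 − 474), about a fifth of the total. Precision would fall short of plan for FQ, KAN, AMK and CAP sensitivity. These figures assume that the Appendix 4 loss and resistance rates hold, that sensitivity is 90% as in Table 2, and that no enrolment beyond 284 + 316 makes up the deficit. The point should be corrected because these are the numbers at which recruitment stops, but it does not call the design into question.

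**What to change.** In the synopsis (study population) and section 5.3.1, replace the enrolment statement with: enrol 360 MTB-positive and 400 additional RIF-resistant patients, to yield at least 284 and 316 evaluable. The protocol will then agree with section 6.1.2, section 9.1, Appendix 4 and SAP section 10.

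Labelling 284 and 316 as evaluable in sections 2 and 3.4 would help clarity but is optional, since neither section uses those figures as enrolment numbers.

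The change is to wording only. The intended size, the staging, the calculation and the analysis stay as they are; the cost is that of a minor protocol revision.
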